Many of the women experience severe menstrual pain, yet undermanage their pain level by not taking a sufficient amount of NSAIDs. Notably, biochemical analyses demonstrate that the administration of naproxen prior to the initiation of the COX-2 cascade results in nearly complete suppression of prostaglandin synthesis; attempting to block synthesis afterwards only leads to a gradual and incomplete suppression.¹ The single, but underpowered trial, comparing menstrual pain relief between prophylactic versus response use to pain with ibuprofen did not find a difference.² It is possible that differences in prophylactic use of naproxen and ibuprofen could be due to different preferential binding to COX-1 and COX-2 receptors. Aside from this trial, clinical investigators have not sufficiently investigated prophylactic use of NSAIDs prior to the onset of menses. Although an educational trial regarding prophylaxis did demonstrate increased patient knowledge, reduction of menstrual pain was not evaluated.³ Therefore, in the present study we will establish whether prophylactic and adequate dosages of Naproxen are capable of reducing menstrual pain more than response use. Secondly, we will establish whether reduction of menstrual pain with optimized naproxen use can reduce bladder pain via cross-organ sensitization or central sensitization. We hypothesize that cross-organ sensitization (COS) is the mechanism by which dysmenorrhea may lead to some forms of chronic pelvic pain. Uterine inflammation during menstruation likely contributes to chronic pelvic pain (CPP) by triggering neurogenic inflammation in adjacent organs.⁴ This COS has been demonstrated with experimental injury and infection in animal models.^{5,6} Our prior findings discussed above^{7,8} motivate our present central hypothesis: *dysmenorrhea produces CPP via repetitive COS episodes.*

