In our ongoing study looking at the relationship between dysmenorrhea, COS and CPP (EH13-094), we planned to determine whether oral contraceptive pills (OCPs), by alleviating menstrual pain could reverse the development of COS. However, our interim analyses of participants in this study identify that many are unwilling to initiate OCPs due to the perceived side effects and fear of hormones. Other interventions to reduce the development of COS also plausibly exist, notably NSAIDs. Therefore, we propose to re-enroll many of the participants from EH13-094 who gave permission for future contact. We will utilize their baseline assessment visit data in order to establish whether naproxen can improve menstrual and bladder outcomes. After consent, prior data will be linked with the current study. We will also open this study to new participants who will be asked to perform a baseline visit (bladder test, pressure tests, EEG, questionnaires and blood draw). Participants will be invited to an open label (non-randomized) prospective trial of naproxen. After six to eight months of diary data, urine monitoring, and blood samples, a repeat visit (bladder test, pressure tests, EEG, questionnaires, and blood draw) will be conducted. The majority of the testing details below have been previously approved for the ongoing study EH13-094.

Additionally, we will investigate whether mechanisms involved in pain sensitivity predict responses to effectiveness of NSAID treatment for menstrual or bladder pain. Several studies identify that women with menstrual pain have central sensory processing abnormalities akin to what is observed in women with chronic pelvic pain states.⁹⁻¹¹ Focused investigation into gynecological risk factors for bladder pain syndrome is of particularly high value, as it more commonly affects women¹², and current treatments, such as pentosan polysulfate,¹³ amitriptyline,¹⁴ or cystoscopic hydrodistension¹⁵ are only modestly effective. The limited efficacy of these treatments reflects the multifactorial mechanisms underlying BPS, particularly in later stages, which may include cross-organ sensitization, central nervous system sensitization, mucosal inflammation, and neuropsychological factors.¹⁶ One underlying hypothesis for this finding is that repetitive episodes of

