dysmenorrhea promote cross-organ or central sensitization. This is supported by clinical observations¹⁷ and experimentally in animal models of provoked uterine inflammation.⁶ Mechanisms involved in central pain modulation can be evaluated with conditioned pain modulation and pressure pain testing^{10,18} and both will be used in this proposal. Additionally, we will look at neural mechanisms using audio and visual tasks¹⁹ with EEG. We will determine whether baseline mechanisms are correlated with menstrual and bladder outcomes. The within subject design also allows us to determine if changes in mechanisms (baseline vs repeat visit) are associated with better outcomes.

Study participants

Inclusion Criteria:

Reproductive-age women (age 18-45) with dysmenorrhea will be recruited. Cases will have: a) average menstrual pain $\geq 5/10$ (0=no pain and 10=the worst imaginable pain) on at least one day during menses or during withdrawal uterine bleeding from cyclic OCs without painkillers, b) menstrual pain in the region between the umbilicus and the perineum, above the level of the inguinal ligament, and c) indication the participant has attempted to resolve pain by medical means (including NSAIDs and/or OCPs). In the circumstance that a participant originally assigned to the dysmenorrhea group does not reach a pain of 5 on any days on the daily diary, this will be handled on a case-by-case basis particularly if they used a continuous around-the-clock, effective pain treatment regimen. Participants who endorse bladder symptoms (subclinical urgency, frequency, bladder pain) on the phone screen or bladder symptoms as reported in EH13-094 will be preferentially recruited (at least 50% of enrolled participants); those who do not endorse bladder symptoms may be determined ineligible. They must not have a formal urological diagnosis such as overactive bladder or painful bladder syndrome.

Exclusion criteria:

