The baseline and follow-up visit includes internal vaginal pressure-pain threshold testing, which is similar in nature to the pelvic floor portion of a gynecological exam. Thus, for participants who have never had a gynecological exam, a study nurse or study doctor may complete a simple exam of the pelvic floor at the screen to promote understanding of the internal vaginal pressure-pain threshold testing that will be completed at the baseline and follow-up visit. This ensures that the integrity of our data is not biased by unfamiliar experience. Participants will be asked whether they have ever had a gynecological exam on the phone screen and a simple exam of the pelvic floor for those that say they have never had an exam will be scheduled into their screen.

Creatinine Test:

A creatinine test will be conducted to check for kidney function for all participants. This will be done via blood draw at the screen visit.

Menstrual Diaries:

All participants will be asked to complete daily diaries for a full menstrual cycle to assess their baseline scores.

[figure not shown]
Baseline Visit:

A baseline visit will be performed for all participants that have not conducted an assessment visit for EH13-094 in the last 12 months: **[Note all of these assessments are the same as the assessments approved in EH13-094]**. The baseline visit will be scheduled to occur during the luteal phase (15 to 25 days after the start of the prior menstrual cycle). Participants will be asked to confirm that menstrual pain or bleeding has not started during the baseline visit.

Food: Baseline Visits are very long so we will offer snacks to the participants (e.g., teddy grahams and fruit roll-ups).

Instrumentation: During the baseline visit, EMG and EKG electrodes, and respiratory rate monitors will be applied and information will be recorded throughout the visit. EMG leads will be placed on the lower abdomen during the bladder testing to measure muscular recruitment. The abdominal EMG leads will be moved to the knees once the bladder pain test is completed. The EKG leads and respiratory belt are placed to measure autonomic activity. The autonomic activity will be recorded to verify nociceptive experience. During each testing session, participants will also have their blood pressure and pulse taken.

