Participants will be instructed on usage of prophylactic and recommended dosage of naproxen. Participants will be instructed to take one Naproxen (500 mg) pill in the morning and one again 12 hours later the first day before their anticipated first day of menses. The research coordinators will help interpret the menstrual pain calendars for the participants to predict their next menstrual cycle. Participants will continue to take a pill twice daily for the first 3 days of their menstrual period. If participants still have menstrual pain the following day, they will be instructed to continue taking 2 pills a day until their pain stops. Any unrelieved pain can be treated with acetaminophen (according to directions listed on the package). Participants will continue taking pills before and during their period for 6-8 months until the follow up visit is performed. In the event that a participant has been taking Naproxen for 3 consecutive days and has been asymptomatic (i.e., not started their menses) we will have them stop taking the study medication. The research staff will instruct them to start taking it again as soon as they start their period.

The dosage does not exceed the maximal daily recommended over the counter dose for Naproxen (1500 mg first day, 1000 mg subsequent days).

Between visit measurements:

Diaries: On each day of menstrual bleeding and/or pain, participants will complete a daily diary. The daily diary will be completed using REDCap and asks them to rate their menstrual, bladder, and bowel pain (using a numeric rating scale where 0-no pain, 10-worst pain imaginable), describe any bleeding, and what time the study medication was taken. They will be asked to record any other pain reliever/medication they tried that day (heat pads, muscle relaxers, herbal teas, etc) in the notes section. They will be instructed to not take any additional painkillers except acetaminophen during their menses or while taking the study medication. Outside of their menses, they can treat their pain however they normally would (flu, headache). To protect confidentiality, subjects will not enter identifying information and only use their assigned subject ID #.

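### The first stated aim, that prophylactic naproxen beats response use, is not what the single-group baseline-to-follow-up comparison estimates

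*Combined protocol and SAP*

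**What the plan says.** The opening background presents the prophylaxis question as unresolved: "The single, but underpowered trial, comparing menstrual pain relief between prophylactic versus response use to pain with ibuprofen did not find a difference". It then commits the study to "establish whether prophylactic and adequate dosages of Naproxen are capable of reducing menstrual pain more than response use", and gives the bladder-pain question as the second aim.

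The design text is different in kind. The study overview, also in the background, says "Participants will be invited to an open label (non-randomized) prospective trial of naproxen" and puts the purpose as to "establish whether naproxen can improve menstrual and bladder outcomes". Under Naproxen, all participants follow one schedule, with the first pills the day before expected menses ("one again 12 hours later the first day before their anticipated first day of menses"), repeated each cycle until follow-up at 6-8 months. Power Analysis/Data Analysis compares diary and questionnaire menstrual pain at baseline with the same measures at 6-8 months. It takes dz=.7 from the historical effect of NSAIDs in general and arrives at n=20, recruiting 30.

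On the baseline cycle, Menstrual Diaries says only: "All participants will be asked to complete daily diaries for a full menstrual cycle to assess their baseline scores". The Inclusion Criteria ask for "indication the participant has attempted to resolve pain by medical means (including NSAIDs and/or OCPs" as evidence of prior treatment. They also allow case-by-case handling of women whose diary pain never reaches 5, "particularly if they used a continuous around-the-clock, effective pain treatment regimen".

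**The concern.** An aim that says one way of using a drug works better than another needs an estimate of the difference between the two. After the background, response use does not appear again as an arm, a period, a defined baseline condition or an analysis. If the aim stands as written, a fall in pain from baseline could be reported as showing that prophylactic, adequate dosing is superior to response use. The same fall could arise whether or not that is true. The protocol itself regards this question as insufficiently investigated, so a wrong answer would matter.

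A smaller matter concerns recording. Dose time is a diary item, but during treatment the diary is required only on days with bleeding or pain. A dose taken on a pain-free day before menses need not be dated anywhere.

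**Working it through.** **1. The plan's own figure.** Inputs from Power Analysis/Data Analysis: dz=.7, alpha .05, power .80, n=20, dropout about 20-30%, recruit 30. Sidedness is not stated; two-sided is assumed. For a paired t-test, power comes from the noncentral t with n-1 degrees of freedom and noncentrality dz × √n.
- n=19: 0.7 × √19 = 3.05, power 82.3%. This is the smallest n that reaches 80%.
- n=20: 0.7 × √20 = 3.13, power 84.4%.
- Dropout: 20/(1-0.20) = 25 and 20/(1-0.30) = 28.6, rounded up to 29. Recruiting 30 covers both.

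The figure reproduces. What it sizes is a within-subject change from baseline.

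**2. What that change contains.** Write R for the study regimen, P for response use and B for whatever the women actually did in the baseline cycle. Then:

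observed change = (R vs P) + (P vs B) + expectancy + regression to the mean + time

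The aim concerns the first term only. The study estimates the sum, and nothing planned separates the terms.
- *P vs B.* This is zero only if baseline use was response use. The text sets no painkiller rule for the baseline cycle. Prior treatment may be NSAIDs, OCPs or both, and continuous use is foreseen for some women. During treatment, by contrast, painkillers other than acetaminophen are barred in menses.
- *Expectancy.* Treatment is open label and pain is self-rated.
- *Regression to the mean.* Entry requires pain of at least 5/10, and a baseline diary that never reaches 5 triggers case-by-case review. Selection therefore also touches the baseline diary.
- *Time.* Follow-up is 6-8 months later, with no concurrent comparison.

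**3. Timing and amount.** The aim names prophylactic and adequate dosing together. Both belong to R vs P as the protocol defines it, so neither is a confounder against that aim.

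**4. Whether dz=.7 carries over.** The documents give no effect size for R vs P. As an illustration only, with values below .7 assumed, a within-subject comparison of the two regimens (two-sided .05, 80% power, before dropout) would need:

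| dz | n needed | power with 20 completers |
|---|---|---|
| 0.7 | 19 | 84% |
| 0.5 | 34 | 56% |
| 0.4 | 52 | 40% |
| 0.3 | 90 | 25% |

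This shows why the n=20 statement should be tied to the pre-post change. It does not measure the defect, which is the absence of the comparison.

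**5. Dating the pre-menses dose.** The evening urine sample is from menses day 2. The single blood draw is on a period day other than the first. Unused pills come back once, at follow-up. None of these dates a pill taken before bleeding. Dosing starts one day before expected menses and stops after three consecutive days without onset, so when menses are on time or late there are 1 to 3 such days per cycle.

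**The case against.** The strongest reply is that the operative plan is consistent. The study overview, the description of a within-subject design and the analysis section all describe a pre-post study. The comparative phrase is one sentence in the rationale, and no test, endpoint or sample size depends on it. The baseline cycle may also be the intended comparator: women must already have sought medical relief, and the background says many take too little NSAID, so usual care could well resemble response use.

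Much of this stands. The analysis section claims only the pre-post comparison, and the sample size needs no change. A reader might infer that baseline cannot represent response use at all. The documents do not support that: the text leaves baseline use undefined, a figure beside the baseline-diary text is not shown, and the clause on continuous regimens is a conditional exception that gives no frequency.

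What does not stand is the idea that the sentence is harmless. It says the study will establish the result, follows directly from the critique of the earlier trial, and is the first of two numbered aims. Even if every woman practised response use at baseline, expectancy, regression to the mean and time would remain.

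On the diary, a reader might infer that early, on-time and late cycles cannot be told apart. Predicted dates from the menstrual pain calendars, set against recorded bleeding dates, could partly classify them. What is missing is the actual dose time on pain-free days, and no planned analysis uses it.

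**Conclusion.** The concern holds as a mismatch between the stated aim and the planned estimate. The first aim claims superiority over response use, the plan estimates open-label change from an undefined baseline, and the aim therefore has no valid planned estimate. The effect falls on what the trial may conclude. The size of the defect is not a percentage: counting treated cycles without response use would not measure it, because in any pre-post design the comparator lies outside the treated cycles.

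Three stronger readings should be set aside. The sample size is not wrong for the comparison it describes. Timing and amount are not confounders against an aim that joins them. The diary gap does not undermine the primary analysis; it is a minor descriptive shortfall.

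The conclusion assumes that the figure not shown does not prescribe response use of naproxen for the baseline cycle. If it did, the comparator would be defined, but expectancy, regression to the mean and time would still be mixed into the change.

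**What to change.** 1. Restate the background aim and the study conclusion as open-label, within-subject change in menstrual pain from baseline, under participants' usual analgesic use, to the study naproxen regimen. Remove the claim of superiority over response use. This matches the purpose already given in the study overview.
2. State in Power Analysis/Data Analysis that dz=.7 refers to this change.
3. Record painkiller name, amount and time in the baseline diary where it does not already do so, to describe the comparator.
4. Minor: require a diary entry with dose time on every study-medication day, including before menses. Use it only to describe how often dosing preceded bleeding.

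The cost is protocol wording, any painkiller items the baseline diary lacks, and about 1 to 3 extra diary entries per cycle, with no added patients or visits. The claim becomes more modest, and prophylactic against response use stays open for a controlled study. Keeping the comparative aim instead would require a defined response-use condition with its own analysis and sample size, for which the documents give no effect size.

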Urine: Participants will be told that urine samples will allow us to verify they are taking the study medication as directed. Participants will be asked to freeze urine collected from the evening of day 2 of their menses for each cycle. 6 storage vials will be provided. The urine samples will allow us to verify if participants are taking the provided pills.

Blood: Participants will be instructed to arrive at Evanston Hospital for a scheduled blood draw 1.5-3 hours after ingesting naproxen pills. This will allow us to verify naproxen is sufficiently absorbed to provide therapeutic effects. Only one naproxen absorption blood draw will be performed per participant. Participants will be allowed to choose the most convenient period day for testing, but cannot come on the first day.

Follow up visit:

Six to eight months later, participants will be invited to return for a follow-up visit. Participants will perform the same measurements obtained in the original baseline visit. In the event participants are unable to return for a complete baseline visit, participants will receive a prorated stipend for partial

completion of items (including questionnaires). Participants will bring in any unused study medication to this visit.

Power Analysis/Data Analysis:

The primary outcomes are menstrual pain and bladder pain. Menstrual pain will be evaluated by comparing diary data and questionnaire data from baseline to 6-8 months after treatment. We estimated the needed sample size with a power analysis. Historically, the effects of NSAIDS are known to have a large effect size ($dz > .7$). A power analysis ($\alpha=.05, 1-\beta=.80$) suggests that to detect a more moderate effect of $dz=.7$ sample size of 20 would be needed. To account for a ~20-30% drop out rate, we will recruit 30 participants.

An additional primary outcome is bladder pain as measured by the experimental bladder pain test and the GUPI questionnaire. We estimated the needed sample size with a power analysis. The effects of oral contraceptives on bladder pain had enormous effect size ($dz=2.9$). Unfortunately, too few participants were willing to take oral contraceptives. A power analysis ($\alpha=.05, 1-\beta=.80$) suggests that to detect a more moderate effect of $dz=1$ sample size of 10 would be needed. We will attempt to attain a sample size of $n=20$ to allow detection of and even lower effect size $dz=0.7$ (per the primary outcome for menstrual pain).

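### The second aim ties a fall in bladder pain to a fall in menstrual pain, but no planned analysis relates the two changes

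*Combined protocol and SAP*

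**What the plan says.** The second aim, in the opening background, reads: "Secondly, we will establish whether reduction of menstrual pain with optimized naproxen use can reduce bladder pain via cross-organ sensitization or central sensitization". In that sentence the agent of change is the reduction in menstrual pain, not naproxen as such. The same section gives the central hypothesis that dysmenorrhea leads to chronic pelvic pain through repeated cross-organ sensitization.

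The design is uncontrolled: "Participants will be invited to an open label (non-randomized) prospective trial of naproxen".

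The Power Analysis/Data Analysis section says "The primary outcomes are menstrual pain and bladder pain" and handles each in its own paragraph. On the first: "Menstrual pain will be evaluated by comparing diary data and questionnaire data from baseline to 6-8 months after treatment". On the second: "An additional primary outcome is bladder pain as measured by the experimental bladder pain test and the GUPI questionnaire". Each is sized through its own paired standardised effect (dz). The menstrual pain calculation is "to detect a more moderate effect of $dz=.7$ sample size of 20 would be needed"; the bladder paragraph gives n=10 for dz=1 and then adopts the same target of 20.

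The other planned analyses concern mechanisms. The background proposes to correlate baseline mechanisms with menstrual and with bladder outcomes, and adds: "The within subject design also allows us to determine if changes in mechanisms (baseline vs repeat visit) are associated with better outcomes". The secondary outcomes relate treatment response to conditioned pain modulation and pressure pain thresholds.

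**The concern.** The aim has two links: naproxen lowers menstrual pain, and that reduction lowers bladder pain. The plan tests the mean change at each end and leaves the second link unexamined. Mean bladder pain could fall among women whose menstrual pain hardly moved, and nothing in the analysis section would show it.

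Other explanations for a fall in bladder pain are open in this trial. Every woman knows she is taking naproxen, so expectation is uncontrolled. Women enter with menstrual pain of at least 5/10, and those with bladder symptoms are preferred (Study participants), so regression to the mean can lower both measures. Follow-up comes six to eight months later, and baseline bladder data for women from the parent study may be up to 12 months old (Study Visits), so natural course also matters. At stake is whether the second aim is answered, or only the narrower question of whether bladder pain changed during naproxen use.

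**Working it through.** **1. The plan's own sample sizes.** Inputs from Power Analysis/Data Analysis: alpha 0.05, power 0.80, dz=0.7 with n=20, dz=1 with n=10. Sidedness is not stated; two-sided is assumed. Power of a paired t-test comes from the noncentral t with n−1 degrees of freedom and noncentrality dz×√n.
- dz=0.7, n=20: noncentrality 0.7×√20 = 3.13; power 84.4%. The smallest n reaching 80% is 19 (82.3%).
- dz=1, n=10: power 80.3%.

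The stated sizes are sound for two separate before-after tests.

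**2. What two positive tests say about the link.** Suppose both outcomes have a true dz of 0.7 and the individual changes are uncorrelated. Each test has power 0.8435, so both are significant with probability 0.8435 × 0.8435 = 0.71. A simulation of 100,000 trials of 20 women, with changes drawn as uncorrelated, also gave 71%. Two significant falls are thus a likely result with no link at all between the changes.

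**3. Search for a linking analysis.** Set side by side:
- Background: baseline mechanisms against menstrual outcomes and against bladder outcomes; changes in mechanisms against better outcomes.
- Secondary outcomes: conditioned pain modulation or pressure pain thresholds against treatment response.
- Primary outcomes: each pain, before against after.

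None has change in menstrual pain on one side and bladder pain on the other.

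**4. How well the missing analysis could perform.** The documents give no expected correlation between the changes, so a range is assumed. By Fisher's z, two-sided power ≈ Φ(atanh(r)×√(n−3) − 1.96). With n=20, √17 = 4.123.

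| Assumed r | atanh(r)×4.123 − 1.96 | Power at n=20 | n for 80% power |
|---|---|---|---|
| 0.3 | −0.68 | 25% | 85 |
| 0.4 | −0.21 | 42% | 47 |
| 0.5 | 0.30 | 62% | 30 |

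For 80% power at n=20, r = tanh((1.960+0.842)/4.123) = 0.59; simulation puts it at about 0.58. Recruiting 30 with 20–30% dropout leaves 24 to 21 women, for whom the figure is 0.55 to 0.58. An observed r of 0.3 at n=20 has a 95% interval of about −0.16 to 0.66. Adjusting for baseline bladder pain costs one more degree of freedom, so these figures are slightly optimistic.

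**5. The correlation of 0.38 quoted for the secondary outcomes.** This matches the one-sided 5% critical value at n=20 (0.378). It is a significance threshold: power at a true r of 0.38 is about 38–39% two-sided. It cannot be borrowed to justify the linking analysis.

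**The case against.** The strongest reply is that the design already does more than two bare before-after tests, and that the remedy cannot separate the rival explanations anyway. Much of this stands.

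- **Direct drug action.** A reader might infer that naproxen is taken throughout, so that plain analgesia would explain any bladder improvement. The documents do not support that. The Naproxen section places dosing around menses. The Baseline Visit section puts the bladder test in the luteal phase, with confirmation that menstrual pain or bleeding has not begun. The Follow up visit section repeats the same measurements, though it does not restate the timing. Direct analgesia is therefore a weaker rival for the bladder test, although it remains plausible for bladder pain rated in diaries on menstrual days.
- **Disconfirmation.** A reader might infer that only a within-woman link could contradict the hypothesis. That is too strong: if menstrual pain fell clearly and bladder pain did not, the planned tests would count against the aim.
- **Mechanisms.** The aim names central sensitization as well as the cross-organ route, and the mechanism analyses address the central route in part.
- **Interpretation.** It is tempting to say that the sponsor would read a mean fall as proof of cross-organ sensitization. The plan gives no interpretation rule, so that would be a guess.
- **Limits of the remedy.** Expectation, regression to the mean, shared reporting and individual responsiveness to naproxen can each move both pains in the same women and produce a slope. A regression cannot replace a control group.

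None of this supplies the missing link. Expectation, regression to the mean and natural course apply to the bladder test and the GUPI alike, and imprecision is a reason to report an interval, not to omit the estimate.

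**Conclusion.** The concern holds in a limited form. The before-after tests are valid and adequately sized, but the second aim as worded goes beyond them. A positive bladder result would support it only weakly; a null one would weigh against it. The 71% figure assumes dz=0.7 for both outcomes, uncorrelated individual changes, 20 completers and two-sided tests. The power figures for the link rest on assumed correlations.

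A reader might go further and make support for the aim conditional on detecting the association. The numbers argue against that: with a real correlation of 0.3 to 0.5, a study of 20 women would miss it in 38% to 75% of cases (100% minus 62% and minus 25%). Floor effects could weaken the slope further, since the plan guarantees bladder symptoms in only half of those enrolled. The conclusion should rest on the estimate and its interval, not on a significance threshold.

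**What to change.** Add one prespecified analysis, labelled exploratory, to Power Analysis/Data Analysis:

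follow-up bladder pain = a + b × (change in diary menstrual pain from the baseline cycle) + c × (baseline bladder pain) + error,

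fitted once with the bladder-test VAS and once with the GUPI. Report b with its 95% confidence interval and no significance rule. State in advance which treated cycles enter the change and whether it uses peak or mean menstrual pain, so that the choice is not made after seeing the data.

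Add two sentences on interpretation. The before-after fall in bladder pain will itself be reported as a change under naproxen. Any statement linking it to reduced menstrual pain or to cross-organ sensitization will be worded as an association and will rest on this estimate and its interval.

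The cost is a few lines of text and a narrower conclusion. The data are already planned: a baseline diary cycle, menstrual pain diaries during treatment, and the bladder test and GUPI at both visits. The drawback is an imprecise slope that shared reporting, expectation or regression to the mean can inflate, so it supports the aim without proving the mechanism.
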